4.4. End of Study Definition

A participant is considered to have completed the study if he/she has completed all phases of the study including the last visit (Visit 7).

The end of the study is defined as the date of the last visit of the last participant in the study.

5. Study Population

Prospective approval of protocol deviations to recruitment and enrollment criteria, also known as protocol waivers or exemptions, is not permitted.

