7.1. Discontinuation of Study Intervention

Participants who are hospitalized during the study period will be allowed to continue in the study until the end at the discretion of the principal investigator and/or the participant. The investigator/participant can decide to discontinue the study drug for safety or efficacy reasons.

Albeit we will invite patients and doctors to stick to the initial treatment unless required by changed medical condition, the specific COPD treatment regimen (LABD(s) without ICS or LABD(s) + ICS) can be changed at any point during the study. Treatment with ICS in the only LABDs group will be permitted if, on clinical Investigators judgement, it would be necessary for patient temporary conditions for at maximum 15 days in case of patient treated at home or for 15 days (at maximum) after hospital discharge in case of hospitalised patient. If the ICS treatment will surpass these periods, the patient will be considered being switched to the LABD + ICS group and considered as protocol violator.

See the SoA for data to be collected at the time of intervention discontinuation and follow-up and for any further evaluations that need to be completed.

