Participants will be asked to complete the CAT and mMRC questionnaires.

Medical history and history of COPD and CV disease will be reviewed and updated as necessary.

Participants will be asked about treatment. Information about any hospitalizations or any unexpected medical events, particularly moderate exacerbations treated with antibiotics and/or steroids will be collected. Information will be obtained by reviewing the patient's medical records and prescribed medication and also from direct questioning of the participant.

The participant's ongoing treatments (concomitant medications) will be reviewed and updated as necessary both for COPD and CV comorbidities, particularly HF, IHD and/or AF. Details of all concomitant medications will be recorded.

Participants will be questioned about the occurrence of any serious adverse events and details will be recorded on the eCRF.

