2.2 Secondary objectives

Secondary objectives are the following:

- to compare the number of moderate/severe exacerbations of COPD in the two patient groups;
- to compare the number of re-hospitalizations and deaths (all cause) in the two patient groups;
- to compare Quality of Life (QoL) scores measured using the COPD Assessment Test (CAT) and modified Medical Research Council (mMRC) dyspnoea scale between the two patient groups;
- to verify if one year of treatment with combination therapy including ICS increases the risk of pneumonia;
- to compare the number of acute cardiac events in this frail, elderly COPD population;
- to compare the incidence of deaths due to cardiovascular events;
- to compare changes in lung function.

3. Study Design

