Treatment effect will be presented as a hazard ratio with the associated 95% Wald CI and p-value.

The following SAS[®] code will be used to estimate the Cox proportional hazards regression model:

```
proc phreg data=dataset;
class CENTER TRT;
model TIME*EVENT(1) = CENTER TRT AGE / ties=exact;
hazardratio TRT / cl=wald;
run;
```

where TIME represents the time to first re-hospitalization and/or death or time to censoring, EVENT the censoring indicator (1 = censored patient), TMT the treatment group, CENTER the center and AGE the age.

The variable TMT will be ordered in SAS in the following order:

- 1 = LABD;
- 2 = LABD + ICS.

Forms			
Title	Statistical Analysis Plan Template		
Code	Version	Effective Date	Page
FRM_ST03_032	02	02 Oct 2017	19 of 26

If the option “ties=exact” requires a considerable amount of computer resources, the Efron approximation will be used (“ties=efron”).

A sensitivity analysis will also be carried out excluding efficacy data (i.e., hospitalization and death) collected after the crossover occurrence date. The same analyses described above will be repeated on this modified dataset.

Finally, the same analyses described above will be repeated in the subgroup of patients treated with triple therapy.

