7.2 Analysis of secondary efficacy endpoints

Definitions and data conventions

Number of re-hospitalizations and death

The number of re-hospitalizations and deaths will be calculated per-subject as the sum of the number of hospitalizations as recorded in the ‘COPD Exacerbation Form’ and the deaths (all cause).

Number of moderate/severe COPD exacerbations

The number of moderate/severe COPD exacerbations will be calculated per-subject as the sum of the number of COPD exacerbations recorded as “Moderate” or “Severe” in the ‘COPD Exacerbation Form’.

Number of pneumonia events

The number of pneumonia events will be calculated per-subject as the sum of adverse events classified with the following System Organ Classes/Preferred Terms:

System Organ Class	Preferred Term
Respiratory, thoracic and mediastinal disorders	
 • Pneumonia NOS • Acute pneumonia • Lung infection • Multilobar pneumonia • Bronchopneumonia • Pneumonia lobar • Pneumonia, organism unspecified • Bronchopneumonia NOS • Acute bronchopneumonia • Community acquired pneumonia • Lobar pneumonia NOS • Ventilator associated pneumonia • Healthcare associated pneumonia • Pneumonia recurrent • Bronchopulmonary infection

Forms			
Title	Statistical Analysis Plan Template		
Code	Version	Effective Date	Page
FRM_ST03_032	02	02 Oct 2017	20 of 26

	
 Pulmonary suppuration Lung infection NOS Pleuropneumonia Bronchopneumonia, organism unspecified Bilateral bronchopneumonia Infectious pneumonitis Nosocomial pneumonia Bronchial pneumonia Bilateral pneumonia Hospital acquired pneumonia Right middle lobe pneumonia Lobar pneumonia
--	---

Number of acute cardiac events

The number of acute cardiac events will be calculated per-subject as the sum of adverse events classified with the following System Organ Classes/Preferred Terms:

System Organ Class	Preferred Term
Cardiac disorders	
 Heart failures -Coronary artery disorders Cardiac arrhythmias Embolic stroke Haemorrhagic stroke Thrombotic stroke

Time on study

Time on study (years) will be calculated using the following formula:

Time on study (years) = (Date of patient completion or withdrawal - Date of randomization +1)/365.25.

Log-time on study (years)

The log-time on study in years will be calculated using the following formula:

$$\text{Log-time on study} = \ln(\text{time on study})$$

Statistical analysis

Analysis will be performed on the ITT population.

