Number of re-hospitalizations and deaths

The number of re-hospitalizations and deaths of all cause (1, 2, 3, 4, >4) will be summarised by using frequency distributions and percentages.

Comparison between treatments will be performed using a Poisson regression model. The model will include the number of events as dependent variable, treatment group and center as qualitative independent variables and age as quantitative independent variable. Log-time on study (in years)

Forms			
Title	Statistical Analysis Plan Template		
Code	Version	Effective Date	Page
FRM_ST03_032	02	02 Oct 2017	21 of 26

will be used as an offset. The overdispersion parameter based on the deviance will be considered in order to account for between-patient variability in the event rate and standard errors will be estimated allowing for extra-Poisson variation.

The number of patients and the number of patients considered in the model will be provided by treatment. P-values of the independent variables based on Wald chi-square test will also be presented.

The adjusted mean rates per patient per year in each treatment group and their 95% CIs will be presented, and the adjusted rate ratio between treatments will be provided with the associated 95% Wald CI and p-value.

The following SAS® code will be used to estimate the Poisson regression model:

```
proc genmod data = dataset;
class TMT CENTER;
model VAR = TMT CENTER AGE / offset=log_time dist=poisson link=log dscale wald type3;
lsmeans TMT / exp cl;
lsestimate 'LABD vs LABD + ICS' TMT 1 -1 / exp cl;
run;quit;
```

where VAR represents the number of re-hospitalizations and deaths, TMT the treatment group, CENTER the center, AGE the age and log_time the logarithm of the time on study in years.

The variable tmt will be ordered in SAS in the following order:

- 1 = LABD;
- 2 = LABD + ICS.

Number of moderate/severe COPD exacerbations

The same analyses described for the number of re-hospitalizations and deaths will be performed for the number of moderate/severe COPD exacerbations (1, 2, 3, 4, >4).

Number of pneumonia events

The same analyses described for the number of re-hospitalizations and deaths will be performed for the number of pneumonia events (1, 2, 3, 4, >4).

Number of acute cardiac events

The same analyses described for the number of re-hospitalizations and deaths will be performed for the number of acute cardiac events (1, 2, 3, 4, >4).

Number of deaths

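### Pneumonia gets no crossover analysis: its one rate model runs by randomised arm past any switch of regimen, and the end of its time at risk is unsettled

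*SAP*

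**What the plan says.** The objective in SAP 2.2 is "to verify if one year of treatment with combination therapy including ICS increases the risk of pneumonia". SAP 7.2 defines the outcome without a time window: "The number of pneumonia events will be calculated per-subject as the sum of adverse events classified with the following System Organ Classes/Preferred Terms". For the analysis it states: "The same analyses described for the number of re-hospitalizations and deaths will be performed for the number of pneumonia events". The model meant is a Poisson regression in the ITT population on treatment group, centre and age, with log time on study as offset. The offset is "Time on study (years) = (Date of patient completion or withdrawal - Date of randomization +1)/365.25".

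Protocol 7.1 says the COPD regimen "can be changed at any point during the study". For the primary endpoint, SAP 7.1 responds to this: "A sensitivity analysis will also be carried out excluding efficacy data (i.e., hospitalization and death) collected after the crossover occurrence date". SAP 7.2 has no counterpart for pneumonia. Protocol 9.3 restricts all efficacy variables other than the primary to the ITT population. SAP 6.1 only lists compliance, and SAP 6.2 foresees no exposure analysis.

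On the end of follow-up, Protocol 4.4 counts a participant as complete when "he/she has completed all phases of the study including the last visit (Visit 7"). Elsewhere Visit 6 is the end of study: in the Visit 6 heading of Protocol Section 8, in Protocol 8.1.7 and in SAP 7.1. SAP 5.3 takes the study-end date from the conclusion form and falls back to Visit 6 if it is missing.

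**The concern.** The objective is about exposure to ICS, but the model compares arms as randomised whatever patients later take. A pneumonia in a LABD patient who has moved to ICS counts against LABD. One in a LABD+ICS patient who has stopped ICS counts against LABD+ICS. For a benefit claim such mixing usually makes the test conservative. For a harm question it works the other way and can make a real increase look small. The SAP treats crossover as a threat for the primary endpoint, but the endpoint on which dilution could hide harm lacks the same check.

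The end of time at risk is a second, separate issue. If the offset runs longer than the collection of pneumonia events, the annual rates are too low.

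**Working it through.** **Inputs.** The documents give no pneumonia rate, expected rate ratio or crossover rate, so there is no planned pneumonia figure to reproduce. The treatment period is 12 months and follow-up adds 3 (Protocol 4.1). Assumed: a true on-ICS rate ratio R; a share a of LABD patients who start ICS and a share b of LABD+ICS patients who stop it, all at month 6; a constant underlying rate; switching unrelated to pneumonia risk.

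**Effect of crossover over 12 months.** A switch at month 6 affects half the year, so a/2 of LABD time is on ICS and b/2 of LABD+ICS time is off it:

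expected ratio = [R(1 - b/2) + b/2] / [(1 - a/2) + R·a/2]

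| a (LABD) | b (LABD+ICS) | R = 1.5 | R = 2.0 |
|---|---|---|---|
| 0% | 0% | 1.50 | 2.00 |
| 10% | 10% | 1.475/1.025 = 1.44 | 1.95/1.05 = 1.86 |
| 20% | 10% | 1.475/1.050 = 1.40 | 1.95/1.10 = 1.77 |
| 30% | 20% | 1.45/1.075 = 1.35 | 1.90/1.15 = 1.65 |

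**What this does to the test.** Assume also 0.05 events per patient-year off ICS, 464 patients per arm each followed for 12 months, R = 1.5 and no overdispersion. Power is Φ(ln(ratio)/√(1/E1 + 1/E2) - 1.96), where E1 and E2 are the expected events.
- No crossover: E1 = 464 × 0.05 = 23.2 and E2 = 23.2 × 1.5 = 34.8. Power is 33%.
- 20%/10% crossover: E1 = 23.2 × 1.05 = 24.4 and E2 = 23.2 × 1.475 = 34.2. Power is 25%.

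Under these assumptions a non-significant ITT result would say little even without crossover, and less with it.

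**End of time at risk.** These texts do not agree:
- End of study: Visit 7 in Protocol 4.4; Visit 6 in Protocol Section 8 (Visit 6 heading), Protocol 8.1.7, SAP 7.1 and the SAP 5.3 fallback.
- Event collection: the schedule of activities reviews non-serious adverse events only up to Visit 6, and the Visit 7 text says "Participants will be questioned about the occurrence of any serious adverse events". Protocol 8.3.1 says all adverse events are collected to the last follow-up visit, at the schedule's time points.

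If a completer's offset is 15 months and no pneumonia is captured after month 12, the rate is multiplied by 12/15 = 0.80, so it is 20% too low. The loss is smaller if serious pneumonia is captured, and there is none for patients who withdraw before Visit 6. The factor is about the same in both arms, so it largely cancels in the ratio.

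**The case against.** Much of the case on the other side stands.

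- **Analysis by randomised arm is legitimate.** This is a pragmatic comparison of strategies, and the ITT rate ratio answers a real question. It should stay. The gap is that nothing accompanies it.
- **The extent of crossover is unknown.** Protocol 7.1 asks patients and doctors to keep to the initial treatment, and LABD patients who exceed the permitted 15 days of ICS count as protocol violators. The ratios above are therefore illustrations.
- **Switching follows clinical need.** It may be related to pneumonia risk, so dilution towards 1 is a tendency and not a certainty. Stopping follow-up at crossover can itself introduce bias.
- **Other comparisons exist.** A reader might infer that the Poisson model is the only between-arm look at pneumonia. It is not: Protocol 9.4.7 compares adverse events by preferred term, and SAP 8.1 tabulates them by treatment group. The model is the only one that uses time at risk, and those tables do not handle crossover. The treatment-received rule in SAP 4.2.4 concerns allocation errors, not later switching.
- **The last three months need not dilute the ratio.** A reader might infer that months 12 to 15 are certainly in the denominator and are time off assigned treatment. The first is unsettled. On the second, Protocol 6.7 says patients are not withdrawn from treatment at month 12. If they keep their month-12 regimen, the extra months lower the ratios for R = 1.5 by only 0.01 to 0.03. Nor can one claim both that events in those months dilute the ratio and that none are captured: the two assumptions exclude each other.
- **Collection after Visit 6 may be better than the schedule suggests.** Visit 7 also asks about hospitalisations and unexpected medical events, and includes a review of records and prescriptions.

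**Conclusion.** The point holds in two parts. First, the only exposure-time model for pneumonia counts time and events after crossover in the randomised arm, and the safeguard designed for the primary endpoint is not extended to it. If ICS raises pneumonia risk, switching will tend to move the ratio towards 1: from 1.5 to about 1.35-1.44 over 12 months under the assumed shares and month-6 timing. The documents support the direction, given that premise and switching unrelated to risk; they do not fix the size.

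Second, the end of time on study is not settled and may not match event collection. At worst, annual rates in both arms are understated by 20%, with little effect on the ratio.

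A reader might go further and infer that the trial is set up to declare ICS free of pneumonia risk. The documents do not support that: SAP 7.2 plans a rate ratio with a 95% confidence interval and p-value, and no conclusion of no harm is pre-specified. This is a gap worth closing because closing it is cheap; the planned ITT analysis is not invalid.

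**What to change.** In SAP 7.2:

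1. Count pneumonia events and time at risk from randomisation to Visit 6 or earlier withdrawal, and use that time as the offset. This removes the Visit 6/Visit 7 ambiguity and matches the period in which non-serious events are scheduled for review.
2. Keep the ITT Poisson model, and add a pre-specified supplementary model in which events and time at risk stop at the crossover date that SAP 7.1 already requires.
3. Report the two side by side. State that switching may be informative, so the supplementary result is not fully protected by randomisation, and that absence of increased risk is not to be inferred from the ITT result alone.

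The protocol passages on study completion and on adverse event collection after Visit 6 should also be reconciled. The cost is SAP wording and one extra model run on dates already needed. The analysis gives up any pneumonia reported between Visits 6 and 7, which can still be listed.

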Secondary	
 to compare the number of moderate/severe exacerbations of COPD in the two patient groups to compare the number of re-hospitalizations and deaths (all cause) in the two patient groups to compare quality of life (QoL) scores measured using the COPD Assessment Test (CAT) and mMRC dyspnoea scale between the two patient groups to verify if one year of treatment with combination therapy including ICS increases the risk of pneumonia to compare the number of acute cardiac events in this frail, elderly COPD population to compare the incidence of deaths due to cardiovascular events to compare changes in lung function 
 number of moderate/severe COPD exacerbations number of re-hospitalizations and deaths (all cause) QoL variation measured as change in CAT total score from baseline to end of treatment period. change in mMRC dyspnea score from baseline to end of treatment period. number of pneumonia events number of acute cardiac events number of cardiovascular deaths change in FEV1 from baseline to the end of treatment period change in FVC from baseline to the end of treatment period

4. Study Design

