9.4.6. Efficacy Analyses

Primary Efficacy Variable

The primary efficacy variable is the time from baseline (Visit 2) to first re-hospitalization and/or death. If the patient discontinues/completes the treatment period and no re-hospitalization and/or death is observed, then the time to first re-hospitalization and/or death is treated as right censored at the end of treatment period (i.e. date of Visit 6) or at the time of the withdrawal during the treatment period (i.e. the date of discontinuation).

The primary efficacy variable will be analyzed using the Kaplan-Meier estimator. Comparison between treatment groups will be performed using the log-rank test stratified by center. A Kaplan-Meier plot for time to first re-hospitalization and/or death will also be presented by treatment group.

The LABD(s)+ICS group will be declared to prolong time to first re-hospitalization and/or death, compared to the LABD(s) group, if the difference between the two treatments is significantly in favour of LABD(s)+ICS (i.e. the p-value from the log-rank test is ≤ 0.050).

In addition, a Cox proportional hazards regression analysis will be performed as well, presenting the treatment effect as a hazard ratio with the associated 95% confidence interval with center, age and treatment group as factors. The inclusion of any other potential confounding factors in the model will be evaluated during the Data Review, verifying the homogeneity of factors distributions among treatment groups.

A sensitivity analysis will be also carried out excluding efficacy data (i.e. hospitalization and death) collected after the crossover occurrence (i.e. patients that switch from one treatment group to the other adding or stopping ICS). The crossover patients that do not experience any hospitalization or death will be considered as censored at the time of cross-over start. Kaplan-Meier, log-rank test and Cox model will be repeated on this modified analysis dataset.

Secondary Efficacy Variables

The number of re-hospitalizations and deaths (all cause) will be analysed using a Poisson regression model. The model will include the number of events as dependent variable and treatment group, age and center as factors. Log-time on study will be used as an offset. The over dispersion parameter based on the deviance will be considered in order to account for between-patient variability in the events rate and standard errors will be estimated allowing for extra-Poisson variation.

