All the other counting variables will be analysed with the same model.

All the continuous variables will be summarized at each visit by means of descriptive statistics. Mean change from baseline value and the 95% confidence intervals will be calculated. P-values of paired t-tests will be provided for mean changes from baseline.

Change in continuous variables will also be analysed using an ANCOVA model, with treatment group, centre and age as factors and baseline as covariate.

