4.8 Changes in the planned analysis

The following changes were implemented in this SAP with respect to the analyses planned in the protocol:

- P-values of paired t-tests will not be provided for the mean change from baseline because the information is considered redundant with the one provided by the 95% confidence intervals.
- Vital signs and physical examination data will be listed only.

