Patients who died will be presented with a breakdown of the causes of death (Cardiovascular death/Other) by treatment and overall.

QoL variation (change in CAT total score from baseline to end of treatment period)

CAT total score, the change from baseline will be summarised by treatment at each visit by means of descriptive statistics. 95% CIs for the mean change will also be calculated.

Forms			
Title	Statistical Analysis Plan Template		
Code	Version	Effective Date	Page
FRM_ST03_032	02	02 Oct 2017	22 of 26

A comparison between treatment groups will be performed with an ANCOVA model with the change from baseline of the CAT total score to the end of treatment period (i.e. Visit 6) as dependent variable, treatment group and centre as qualitative independent variables and age and baseline value of the variable as quantitative independent variables.

The number of patients and the number of patients considered in the model will be provided by treatment. P-values of the independent variables will also be presented.

The adjusted means for treatments and the relative 95% CIs will be presented. The difference between the adjusted means for LABD and LABD + ICS will be calculated with the relative 95% CI and p-value.

The following SAS® code will be used to estimate the ANCOVA model:

```
proc mixed data = dataset;
class TMT CENTER;
model CHG = TMT CENTER AGE BASELINE;
lsmeans TMT / cl;
lsestimate 'LABD vs LABD + ICS' TMT 1 -1 / cl;
run;
```

where CHG represents the change from baseline of the CAT total score at Visit 6, TMT the treatment group, CENTER the center, AGE the age and BASELINE the baseline value of the variable.

The variable TMT will be ordered in SAS in the following order:

- 1 = LABD;
- 2 = LABD + ICS.

Change in mMRC dyspnea score from baseline to end of treatment period

The same analyses described for the change in CAT total score will be performed for the change in mMRC dyspnea score.

Change in FEV1 from baseline to the end of treatment period

The same analyses described for the change in CAT total score will be performed for the change in FEV1.

Change in FVC from baseline to the end of treatment period

The same analyses described for the change in CAT total score will be performed for the change in FVC.

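### SAP 7.2 plans no between-arm comparison of cardiovascular deaths, although the objective is to compare them and the protocol's general rule for counts implies a model; SAP 4.8 does not declare the change

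*SAP*

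**What the plan says.** **Objective and endpoint.** Protocol section 3 (Objectives and Endpoints) lists "number of cardiovascular deaths" as a secondary endpoint. The SAP carries it into its secondary efficacy list (3.5.2) and keeps the matching objective in 2.2: "to compare the incidence of deaths due to cardiovascular events".

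**Protocol analysis.** Section 9.4.6 states: "The number of re-hospitalizations and deaths (all cause) will be analysed using a Poisson regression model". The model has treatment group, age and center as factors and log-time on study as offset. The section then adds: "All the other counting variables will be analysed with the same model".

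**SAP analysis.** Section 7.2 repeats the Poisson analysis by name for the other counts, for instance "The same analyses described for the number of re-hospitalizations and deaths will be performed for the number of acute cardiac events". Under its heading for number of deaths, the whole plan is: "Patients who died will be presented with a breakdown of the causes of death (Cardiovascular death/Other) by treatment and overall".

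**Declared changes.** SAP 4.8 opens with "The following changes were implemented in this SAP with respect to the analyses planned in the protocol" and lists two items. The first begins "P-values of paired t-tests will not be provided for the mean change from baseline"; the second limits vital signs and physical examination to listings. Neither concerns deaths.

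**The concern.** The objective is to compare, but a table of deaths by cause and arm is a description. It carries no effect estimate, no interval and no test, so a team that follows the SAP exactly will report nothing that answers this objective.

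The endpoint matters here. Every participant must have heart failure, ischemic heart disease or atrial fibrillation (Protocol 5.1), and the introduction cites both cardiovascular risk with long-acting bronchodilators and fewer major cardiovascular events with an ICS-containing triple combination. Readers will look for the cardiovascular death result. If no comparison is fixed beforehand, any that appears later in this open-label trial will have been chosen after the data were seen.

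The change is also silent. Section 4.8 records even the loss of paired t-test p-values, so its silence on deaths would lead a reader to think that the protocol's plan for this endpoint still stands.

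**Working it through.** **1. The nine secondary endpoints in SAP 3.5.2 set against SAP 7.2**

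| Endpoint | Between-arm analysis in SAP 7.2 |
|---|---|
| Re-hospitalizations and deaths (all cause) | Poisson: rate ratio, 95% CI, p-value |
| Moderate/severe exacerbations | same Poisson analysis |
| Pneumonia events | same Poisson analysis |
| Acute cardiac events | same Poisson analysis |
| Change in CAT | ANCOVA: difference, 95% CI, p-value |
| Change in mMRC | same ANCOVA |
| Change in FEV1 | same ANCOVA |
| Change in FVC | same ANCOVA |
| Cardiovascular deaths | none; breakdown by cause and arm |

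Four of the five counts have a model, all four continuous endpoints have one, and cardiovascular death has none.

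**2. Is it covered elsewhere?** The primary endpoint and the re-hospitalization and death count use death from any cause. The acute cardiac count is built from adverse-event terms, not from cause of death. The chi-square and Fisher tests in SAP 8.1 are for adverse-event categories. None gives an effect specific to cardiovascular death.

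**3. What is lost: illustration only.** The documents give no expected number of cardiovascular deaths, so the counts below are assumptions. The only input from the documents is 516 randomised per arm (Protocol 9.2). With *a* deaths on LABD, *b* on LABD+ICS and *n* per arm:

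RR = *b*/*a*; SE(ln RR) = √(1/*a* + 1/*b* − 2/*n*); 95% CI = exp(ln RR ± 1.96 × SE).

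For 15 v 9: RR = 9/15 = 0.60; SE = √(0.0667 + 0.1111 − 0.0039) = 0.417; CI = exp(−0.511 ± 0.817) = 0.26 to 1.36.

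| Assumed deaths, LABD v LABD+ICS | Planned table shows | A comparison would show | Fisher p |
|---|---|---|---|
| 15 v 9 | 2.9% v 1.7% | RR 0.60 (0.26 to 1.36) | 0.30 |
| 26 v 15 | 5.0% v 2.9% | RR 0.58 (0.31 to 1.08) | 0.11 |
| 12 v 12 | 2.3% v 2.3% | RR 1.00 (0.45 to 2.21) | 1.00 |
| 9 v 15 | 1.7% v 2.9% | RR 1.67 (0.74 to 3.77) | 0.30 |

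SAP 7.2 analyses the ITT set, which by definition cannot exceed the number randomised. The denominator hardly matters at these counts: with 464 per arm, the 15 v 9 interval is 0.265 to 1.357, against 0.265 to 1.359 with 516.

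**4. Precision by total deaths *D*, split evenly (assumed).** SE of the log rate ratio ≈ √(4/*D*), so the 95% CI around a ratio of 1 is exp(±1.96 × √(4/*D*)):

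- *D* = 10: 0.29 to 3.45
- *D* = 20: 0.42 to 2.40
- *D* = 40: 0.54 to 1.86
- *D* = 60: 0.60 to 1.66

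An estimate would be imprecise across this range, but it can be computed.

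**The case against.** **The protocol never names a model for cardiovascular death.** This stands. The plan comes from one general sentence about counting variables, and per patient this endpoint is 0 or 1, so it fits a Poisson count poorly. A reader might infer that the SAP deleted an analysis written expressly for this endpoint; the protocol does not support that. But the endpoint is worded as a number, the sentence makes no exception, and the SAP itself keeps the aim to compare.

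**Nothing is hidden.** This also stands in part. Counts by arm are planned, and SAP 4.1 adds percentages for categorical variables. A reader might infer that the trial's readers are left with no means of judging uncertainty. That goes too far, since a crude risk ratio and interval follow from the counts and arm sizes, as shown above. What is missing is a comparison that is pre-specified and reported.

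**The impact is limited.** Agreed. This is one of nine secondary endpoints, no power is claimed for it, no multiplicity adjustment is planned, and acute cardiac events do get an adjusted rate ratio. That ratio answers a different question.

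**There may be too few deaths to model.** Possibly, but the SAP does not give this as a reason, and sparse events make an interval more useful.

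**Conclusion.** The SAP departs, without declaring it, from what the protocol's general rule implies for a named secondary endpoint, and it leaves a stated secondary objective without an estimate, interval or test. This rests on reading the number of cardiovascular deaths as one of the protocol's counting variables. The mismatch within the SAP, between its aim to compare and its descriptive plan, does not depend on that reading.

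The point should be corrected, but it does not threaten the trial: the primary analysis and the other eight secondary endpoints are untouched. No magnitude can be taken from the documents. The illustrative counts are assumptions, run in both directions, and show only that a bare difference such as 2.9% v 1.7% can be compatible with no effect. They do not show that any conclusion would change.

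**What to change.** In SAP 7.2, add one between-arm comparison of cardiovascular death, by randomised arm, with a 95% CI. Either of these would serve:

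- a cause-specific hazard ratio over the 12-month treatment period, with the same start and censoring dates as the primary endpoint and other deaths censored, stating that a re-hospitalization does not end follow-up for this endpoint; or
- a risk difference with exact 95% CI and Fisher's test.

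Choose one before the data are seen. If the second is to be a fallback for sparse events, give a numeric event threshold, because a phrase such as too few events leaves the choice until after the counts are known. State the observation window explicitly, since participants are followed for 15 months but treated for 12.

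In SAP 4.8, record that this replaces the protocol's Poisson model, with the reason that a patient can die only once. If the sponsor prefers descriptive reporting, the minimum is to declare and justify it in 4.8 and to bring the objective in 2.2 into line.

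Cost: SAP wording, including window and censoring rules, and one extra table. The interval will probably be wide.
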